1. PROTOCOL SYNOPSIS

Title:	Phase 2, Single Arm, Historically Controlled Study Testing The Safety and Efficacy of Adjuvant Temozolomide plus TTFields (Optune®) plus Pembrolizumab in Patients with Newly Diagnosed Glioblastoma (2-THE-TOP)		
Drug/Device	Pembrolizumab, temozolomide, and TTFields (Optune®)		
Study Objectives:	To determine whether the addition of pembrolizumab to the combination of TTFields (Optune [®]) and adjuvant temozolomide (Triple Combination) increases progression-free survival (PFS) in patients with newly diagnosed glioblastoma (GBM) as compared to historical control data in EF-14 study.		
Study Design:	Open-labeled, historically controlled		
Study Hypothesis:	The hypothesis of this study is that the addition of pembrolizumab to the combination of TTFields (Optune ®) and adjuvant temozolomide (TMZ) will significantly increase the PFS of newly diagnosed GBM patients compared to a historical control.		
Sample Size:	24 patients with newly diagnosed GBM		
Study Population:	Patients 18 years and older with pathologic diagnosis of GBM WHO Grade IV who have undergone maximal resection or biopsy followed by radiation therapy with concomitant temozolomide (Stupp protocol) [1]		
Primary Endpoint:	To determine whether the triple combination of pembrolizumab when added to TTFields (Optune ®) and adjuvant temozolomide increases PFS in patients with newly diagnosed GBM as compared to historical control data in the EF-14 study.		
Secondary Endpoint:	 To determine toxicity and tolerability of the triple combination in newly diagnosed GBM patients To determine overall survival (OS) and radiographic response (RR) of the triple combination in newly diagnosed GBM as compared to historical data in EF-14 study To determine whether pembrolizumab augments TTFields-initiated glioma-specific immune reaction. 		
Exploratory endpoints:	 Metabolomics signature of immune activation by TTFields and TTFields + pembrolizumab in serum and urine. To determine if mutation burden, when available from standard of care genomics analysis, in primary tumor samples correlates with response to pembrolizumab in the presence of TTFields. To determine if intratumoral expression of PD-L1 correlates with response to pembrolizumab in the presence of TTFields. 		
Sponsor:	Novocure Ltd. [name]		

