3. OBJECTIVES

This prospective, single-arm, open-label study will be conducted in patients with newly diagnosed GBM who have completed standard of care radiation therapy together with concomitant TMZ. In this protocol, we propose to combine **TTFields** (utilizing the Optune System) with **pembrolizumab** during the adjuvant **TMZ** treatment phase for newly diagnosed GBM. We hypothesize that TTFields combined with TMZ will elicit anti-mitotic effects on proliferative cancer cells and also significantly augment recruitment of immune effector cells specific for glioma cells to the tumor microenvironment where pembrolizumab, a PD1 inhibitor, further potentiates the glioma-specific immune reaction to achieve a synergistic therapeutic effect.

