3.3 Exploratory Objectives

- 1. Metabolomics signature of immune activation by TTFields and TTFields + pembrolizumab in serum and urine.
- 2. To determine if mutation burden, when available from standard of care genomics analysis, in primary tumor samples correlates with response to pembrolizumab in the presence of TTFields.
- 3. To determine if intratumoral expression of PD-L1 correlates with response to pembrolizumab in the presence of TTFields.

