6. TREATMENT PLAN

Patients with newly-diagnosed GBM who undergo maximal safe resection (biopsy alone is eligible) followed by chemoradiation consisting of concomitant TMZ 75mg/m² daily and RT with minimal RT dose of 40gy will be eligible for this trial. MGMT methylation status will be recorded.

Four weeks (+7/-14 days) after completing chemoradiation, patients will undergo baseline standard of care MRI. Four to six weeks after finishing chemoradiation, patients will start monthly cycles of adjuvant TMZ. A minimum of 6 and maximum of 12 cycles of adjuvant TMZ will be given depending on tolerability and toxicity.

Treatment with Optune will start at approximately the same time as the first cycle of adjuvant TMZ and continue until second disease progression or a maximum of 2 years. Urine specimens will be collected as well as peripheral blood mononuclear cells (PBMC) will be obtained and cryopreserved at time points specified. No sooner than 3 weeks after starting Optune therapy, patients will begin open-label treatment with pembrolizumab 200mg IV every 3 weeks until first disease progression or unacceptable toxicities or 2 years, whichever comes first.

At first progression, patients will be allowed to continue with Optune therapy combined with any other therapy, which may include pembrolizumab, per standard of care at the discretion of the treating physician. Surgical resection or biopsy of first recurrent tumor for confirmation of recurrence is allowed within the protocol.

For correlative studies, flash frozen tumor tissues, where available, will be used to prime dendritic cells. Intratumoral PD-1 expression will also be determined by IHC using FFPE slides. Research blood will be drawn prior to starting adjuvant therapy and within approximately 1 week before the first dose of pembrolizumab. Subsequently research blood will be drawn prior to the second dose of pembrolizumab, and at approximately 2-, 4-, 6-, 12-, and 24-months (+/- 2 weeks) post-pembrolizumab dosing. Urine samples will be obtained at the same time points as research blood. If there is evidence of progression, however, a final research blood draw and urine sample will be obtained within 30 (+/- 7) days of progression and no further research blood draw and urine specimen will be performed (unless the patient continues on Optune therapy to second progression as detailed in the paragraph above). Research blood will also be collected before resection or

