10.4 Data Analysis Considerations (Protocol v10.1)

[name], sub-Investigator at USC, will assist with secondary analysis of coded clinical data for primary and secondary endpoints. A coded limited data set will be shared for purposes of data analysis and a data use agreement (DUA) will be included as part of the statement of work. Data will be stored in UF Box and [name] and his designee will be provided access via UF institutional procedures. The LDS will be transferred to USC and will be stored on secure, duallyauthenticated USC servers with limited access only to [name] and his designees. Analyzed data files will also be password protected and stored on password protected computers.

Additionally, [name] will perform correlative studies which include expression analysis of peripheral blood mononuclear cells (PBMCs) and tumor samples to determine if correlations in expression of key gene pathways with the clinical outcome of enrolled subjects with newly diagnosed GBM receiving the study treatment of adjuvant temozolomide + TTFields + pembrolizumab. PBMCs and tumor samples will include the subject's study ID, sample type and timepoint and date of collection. A corresponding coded limited data set that includes subject ID, dates associated with the individual, clinical data/survival data, treatment history and detailed response data will be shared with [name] in order to accurately identify and characterize signatures of response. We will treat survival in the 2THETOP data as a continuous variable and

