develop computational models that incorporate all key clinical and molecular characteristics to define response signatures that are also continuous with correlation with survival. We plan to apply novel computational bioinformatics to identify cytotoxic T lymphocyte (CTL) clones that are shared between the tumor microenvironment (TME) and the periphery prior to treatment and at the time of radiographic changes and between pathologically proven immune changes and true recurrence. The goal is to identify T cell clones that were expanded after treatment and capable of infiltrating the TME to induce productive anti-tumor immunity. This information will help determine if immune resistance is a function of changing of the "guards" or changing in the TME's immunosuppressive functions. Each TCR clone will be paired with its expression profile to allow for the identification of the master regulatory subnetwork specific in these TME access-enabled tumor-specific CTL clones as compared to those that were expanded in the periphery but failed to reach the TME. Next, we plan to answer the following questions: 1) What defines the systemic signal created by study treatment? 2) What systemic signals distinguish objective responders from non-responders? and 3) What systemic signals may prevent non-responders from responding? For example, in certain non-responders, is it because their immune system also activates an alternate immune checkpoint (e.g., LAG3, CTLA4, IDO1, TGIT etc.) in addition to PD-1/PD-L1? and if so, will using a combination of checkpoint inhibitors be more effective? The answers to these questions will help us develop a more robust signature that can predict response and guide subsequent TTFields-based combination therapy. Clinical data will be stored in UF Box and [name] and his designee will be provided access via UF institutional procedures. Sequencing data will be raw RNAseq and DNA sequences in FASTQ format. The raw sequencing data from all correlative studies for 2THETOP are stored in UF HiPerGator. UF will initiate the transfer to USC using Globus (which is a highly secure and fast transfer system frequently used in high data content transfer). Sequencing and associated clinical data will be stored on secure dually-authenticated USC supercomputer and servers with limited access to only [name] and his designees. Analyzed data files will also be password protected and stored on password protected computers.

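### The response signature in section 10.4 is defined by correlation with survival in a single arm, so a score that only reflects baseline prognosis can qualify and cannot support a claim of response to treatment

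*Combined protocol and SAP*

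**What the plan says.** Section 3 sets the design: "This prospective, single-arm, open-label study will be conducted in patients with newly diagnosed GBM". The synopsis gives the size as "24 patients with newly diagnosed GBM".

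Section 10.4 gives the rule for the signature. It begins "We will treat survival in the 2THETOP data as a continuous variable and" and continues "develop computational models that incorporate all key clinical and molecular characteristics to define response signatures that are also continuous with correlation with survival". The analyst receives "A corresponding coded limited data set that includes subject ID, dates associated with the individual, clinical data/survival data, treatment history and detailed response data", all from enrolled subjects. No clinical variables are listed or excluded. Those available include MGMT (section 6: "MGMT methylation status will be recorded"), KPS and steroid dose (section 6.4), and biopsy versus resection (section 4.1).

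The same section then poses three numbered questions: what systemic signal the treatment creates, what separates objective responders from non-responders, and what may stop non-responders from responding. Of the answers it says that they "will help us develop a more robust signature that can predict response and guide subsequent TTFields-based combination therapy".

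In section 3.3, exploratory objectives 2 and 3 each ask whether one marker (mutation burden, PD-L1 expression) "correlates with response to pembrolizumab in the presence of TTFields".

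Sections 10.1 and 10.2 use the EF-14 control for PFS, OS and radiographic response only. For the signature the document describes no comparison group, clinical-only base model or external data set.

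**The concern.** A response signature should identify patients whose outcome differs because of the treatment. The rule in 10.4 tests something else, namely whether a score is related to survival among patients who were all treated alike. A patient with favourable baseline features lives longer with or without pembrolizumab, and a score that encodes those features satisfies the rule. Placing clinical characteristics in the same model as the molecular ones makes this easier, and the plan has no step that shows how much the molecular part adds. Validating the score would not help, because a prognostic score validates well.

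At stake is the wording and later use of the correlative result: ordinary prognosis could be reported as a signature of response to the study treatment.

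**Working it through.** **The plan's own figure.** The documents give no number for the signature. The only design figure is the detectable PFS gain of 6 to 8 months in section 10.3. It reproduces: for a one-sample log-rank test under Weibull proportional hazards, gain = 6.7 × (HR^(-1/k) − 1). Solving for 80% power at one-sided 0.05 with n=24 gives 7.6, 6.7 and 5.9 months at k = 0.82, 0.88 and 0.95. For example, at k=0.88 the HR is 0.542, the median 13.44 and the gain 6.74. This figure has no bearing on the signature.

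**What a single arm can identify.** Let x be a score and A the treatment indicator:

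hazard = h0(t) × exp(βx + θA + γxA)

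β is prognosis, θ the common treatment effect, and γ the differential benefit that a predictive claim needs. With A=1 for everyone this becomes

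h0(t)·exp(θ) × exp((β+γ)x)

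θ is absorbed into the baseline hazard and only β+γ can be estimated. A correlation with survival is therefore compatible with γ=0.

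**Illustration of size.** From the documents: n=24 and 12-month accrual (10.3), median OS 20.9 months (2.1), follow-up of 18 months (10.3) or 60 months (five-year survival follow-up, 6.6). Assumed, because the documents give none: exponential OS, the same treatment effect in everyone, prognostic SD σ of 0.3, 0.5 or 0.8 on the log-hazard scale, a two-sided 0.05 test, and a signature equal to (clinical + molecular)/√2.

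Hazard = ln2/20.9 × exp(σ·clinical + b·molecular), censored at follow-up plus a uniform 0-12 months. With b=0 the molecular score is noise. Share of trials with p<0.05:

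| Score tested (b=0) | 18 months, σ = 0.3 / 0.5 / 0.8 | 60 months, σ = 0.3 / 0.5 / 0.8 |
|---|---|---|
| Equal mix of clinical factor and noise | 11% / 22% / 42% | 16% / 29% / 51% |
| Clinical factor alone | 19% / 40% / 76% | 24% / 55% / 86% |
| Noise score, added to the clinical score (nested test) | 6-7% | 6-7% |

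With σ=0 the rejection rate is 5-6%. Repeat runs moved these figures by a point or two; the nested rate stayed within about 5-8%.

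**Second check by rank correlation.** Weibull survival with k=0.88, 24 patients, no censoring and a purely prognostic score. At assumed HRs per SD of 0.74, 0.61, 0.50 and 0.37, the mean rank correlation with survival is about 0.24, 0.37, 0.48 and 0.60, with p<0.05 in about 21%, 45%, 69% and 90% of trials. Results agree within simulation error whether the common treatment HR is 1.0 or 0.6, as the algebra requires.

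**What a nested test does and does not do.** Set b=0.7, still with identical treatment benefit in everyone. The molecular score is then itself purely prognostic, yet it passes the nested test in about 61-67% of trials at 18 months and 75-78% at 60 months. The nested test separates the molecular from the clinical contribution. It does not separate prognostic from predictive.

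**Form of the clinical adjustment.** The 6-7% is for one clinical score with fixed weights. If five clinical terms are fitted freely in 24 patients, the nested false-positive rate is about 9-13%.

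**The case against.** Several points on the other side stand.

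- **Guiding therapy.** A reader might infer that the survival-correlated score is itself to guide therapy. The documents do not say that. The sentence about guiding later combinations refers to the answers to the three numbered questions, and no decision in this protocol uses a signature.
- **Section 3.3.** A reader might also infer that section 3.3 has the same defect. It does not: those objectives take one marker at a time against response, which has its own criteria in section 13.4. They and the responder questions share only the general single-arm limit.
- **Existing wording.** Section 10.4 already states part of its aim modestly, as correlating gene expression with the clinical outcome of treated subjects. The response-signature wording a few lines later goes beyond that.
- **Reading of the model.** Incorporating clinical and molecular characteristics could mean a multivariable model with clinical terms as adjustment. Section 10.4 fixes no weights, no collapsed score and no significance test, so the percentages illustrate one reading under assumed prognostic strengths. That the clinical variables would be prognostic is itself an inference, since none is listed.
- **Nested model.** It might be taken to cure the problem. It does not, as the b=0.7 result shows.
- **Scope.** The work is correlative, and the limitation is common to single-arm marker studies.

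None of this removes the core. Under either reading of the model only β+γ can be estimated, and 10.4 does not say so. The before-and-after comparisons in sections 7.1.2 and 7.3.2 can show change on treatment, but not who benefits because of it.

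**Conclusion.** The point holds as a limit on what may be concluded. As defined in 10.4, a response signature can be met by a score that merely reflects baseline prognosis, so it cannot support a claim about response to, or benefit from, the study treatment. This follows from the single-arm design and does not depend on the simulation.

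The size (11-42% at 18 months and 16-51% at 60 months for a half-clinical, half-noise score, against 6-7% for the nested test) is illustrative. It rests on an equal-weight score, one prognostic factor with assumed SD 0.3 to 0.8, exponential survival and a 0.05 test that the plan does not specify. The primary PFS analysis is not affected. This is a low-cost improvement that should be made.

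**What to change.** 1. **Section 10.4, analysis.** Report the molecular signature's added association with survival over one base clinical score (nested Cox likelihood-ratio test). Fix the score's variables and weights, and the source of the weights, before the molecular data are examined. Do not fit several clinical terms freely in 24 patients. State a rule for missing MGMT: section 4.1 asks for it only if available and covers indeterminate results, but not absent ones. Describe the result as added prognostic association only.

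2. **Sections 10.4 and 3.3, wording.** Describe the results as association with outcome on the triple combination. State that a single arm cannot separate prognostic from predictive markers, and that any use to guide later therapy needs testing in a data set with a comparison group.

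**Cost.** Wording, one nested model and agreement on the base score; no new patients, samples or visits. Fewer signatures will reach significance and the conclusion will be more modest. With a molecular log-HR of 0.7 per SD at 18 months, the nested test is significant in 62-64% of trials against 62-92% for the combined score, but that gap comes from counting clinical prognosis as molecular signal.

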11. STUDY CALENDAR

	Screening	Week 0 (TMZ/ Optune Cycle 1)	Week 4 (TMZ/ Optune Cycle 2, Pembro Dose 1)	Week 7 (Pembro Dose 2)	Week 8 & every 4 weeks on-treatment management (TMZ Cycles 3-12)	Week 10 & every 3 weeks on-treatment management (Pembro Dose 3 and beyond)	Post TMZ Treatment follow-up	Post- Pembro Treatment follow-up	Post treatment termination
Informed Consent	X^1								
Medical History	X^{12}								
Pregnancy Test	X^{17}								
PBMC & Urine	X^{18}			X^{18}				X^{19}	
Specimen									
Physical Exam, KPS	X^8		X^8	X^8		X^8	X^8	X^8	
Tumor Tissue	X^{21}							X^{22}	
PT/PTT, INR		X^{23}	X^{23}		X^{23}		X^{23}		
CBC with Differential	X	X^9	X^9		X ⁹		X^{15}	X	
CMP	X	X^{10}	X^{10}	X^{10}	X^{10}	X^{10}	X^{15}	X	
TSH/Free T4	X		X^{11}	X^{11}		X ¹¹	X^{15}	X	
MRI	X^2				X^{13}		$X^{13, 20}$		
Temozolomide Cycle		X^3	X^4		X^4				
Pembrolizumab			X ⁵	X^5		X^5	X^5		
Optune		X^6	X^6		X^6				
Optune Compliance			X^6					X	
AE Assessment	X^7	X^{16}	X^{16}		X^{16}			X	
Concomitant	X	X	X	X	X	X		X	
Medications									
Survival Contact									X^{14}

- 1. No study-specific procedures are to be performed prior to obtaining informed consent. However, assessments performed according to SOC prior to consent may be used to fulfill the screening requirement. Study treatment should start no later than 6 weeks from last dose of concomitant Temozolomide or radiation therapy (the latter of the two).
- 2. Patients will undergo SOC brain MRI scans with RANO disease/response evaluation at screening, 4 weeks (+7/-14 days) after end of chemoradiation.
- 3. Patients will begin treatment with temozolomide at 4 weeks (+14 days) from end of radiotherapy, week 0. Cycle 1 will be dosed at 150mg/m² daily for 5 consecutive days of a 28-day cycle.
- 4. Patients will begin treatment with temozolomide Cycle 2 and subsequent cycles every 4 weeks (+7 days) at 200mg/m² PO daily for 5 consecutive days, unless toxicity occurs. See 6.3.1 for dose escalation parameters.
- 5. Pembrolizumab will be given every 3 weeks (+/- 4 days) beginning no sooner than 3 weeks from the start of Optune. For subjects who receive pembrolizumab alone after the completion of TMZ or due to TMZ intolerance, pembrolizumab infusions may be administered per the treatment plan if absolute neutrophil count (ANC) is $\geq 1.0 \times 10^9$ /L, and the platelet count is $\geq 50 \times 10^9$ /L, and if it is determined by the treating physician that the cytopenia was unlikely to be related to pembrolizumab treatment.
- 6. Optune treatment will begin at Week 0 (+7 days) and will be continuous throughout study. Compliance documentation will be obtained every 4 weeks (+/- 7 days).
- 7. The adverse event-reporting period will begin immediately following initiation of treatment with the adjuvant treatment with TMZ and the Optune device.
- 8. Physical exam and KPS will be performed prior to the first and second dose of pembrolizumab, and every 3 weeks (+/- 4 days) to coincide with each subsequent pembrolizumab dose while on TMZ adjuvant therapy, then every three pembrolizumab dose thereafter. Neurological status will be included as part of the assessment.
- 9. CBC with Differential will be performed within 3 days prior to starting each cycle of temozolomide.
- 10. CMP will be performed prior to each cycle of pembrolizumab and prior to starting each cycle of temozolomide (+/- 7 days). When temozolomide and pembrolizumab are given within 3 days of each other, only one set of CMP will be done for both drugs.
- 11. TSH/Free T4 will be performed prior to the first infusion of pembrolizumab and then prior to every other pembrolizumab infusion thereafter.
- 12. Medical history may be performed at any time prior to registration.
- 13. Patients will undergo SOC brain MRI scans with iRANO response evaluation every 2 months (+/- 7 days) until second progression.
- 14. All patients will have their survival status documented every 3 months (+/- 1 month) for up to 5 years or death, whichever occurs first. Survival information can be obtained via telephone or from clinic notes.

- 15. If study treatment is ended due to disease progression or toxicity prior to the 24 months study term, a final research blood draw will be obtained within 30 (+/- 7) days of progression and no further research blood draws will be performed.
- 16. The AE reporting period will be continuous throughout the study, ending at least 30-days following last study treatment (Pembrolizumab dose, Temozolomide dose, or wearing Optune, whichever comes last).
- 17. Either serum or urine testing accepted.
- 18. Research blood draws and urine samples will be obtained prior to start of study intervention, prior to first and second dose of pembrolizumab (-14 days), 2-, 4-, 6-, 12-, and 24-months after the first dose of pembrolizumab (-7 days each dose). See section 7.1.1.
- 19. A final peripheral blood mono-nuclear cells will be drawn and urine specimen will be collected after end of study treatment see Section 7.1.1
- 20. In the case of clinical progression, an MRI will be obtained within 7 days of the treating physician becoming aware.
- 21. Verification of tissue availability and location needs to be determined during screening so that it can be retrieved at a later time.
- 22. Collection of recurrent tissue and research blood if the patient has a resection or biopsy.
- 23. For patients receiving relevant anti-coagulants only

